- **Specify objectives and hypotheses to be tested in the research project**

Aim 1: Pilot test, in a randomized controlled design (N=120, 60 in each group), the effect of *ED GOAL* administered by trained nurses on patient and caregiver ACP engagement one month after leaving the ED.

Hypotheses: ACP engagement (a composite outcome combining patient-reported and EMR outcomes) will significantly increase in those who received *ED GOAL* compared to usual care.

Aim 2: Identify the patient-perceived benefits and obstacles of ACP conversations after *ED GOAL* using semi-structured interviews (N~30).

[figure not shown]
Rationale: Most patients who underwent our intervention in prior studies expressed their gratitude and reported how helpful the intervention was in their lives. Yet, these perceived benefits (“opened my eyes about what I need to focus in my life”) may be difficult to capture using validated, quantitative instruments. Furthermore, we will also elicit patient-perceived barriers to completing the ACP conversations.

3. General Description of Study Design

- **Explain the basic study design, e.g., parallel group, randomized controlled trial, open-label single arm study, cross over, adaptive, etc.**

This is a two-armed, parallel-design, pre-/post-intervention assessment study. We will conduct a randomized controlled trial for *ED GOAL* on a cohort of 120 older adults with serious illness to collect patient-centered outcomes and determine preliminary efficacy on increasing ACP engagement (self-reported and/or in the electronic medical record) one month after leaving the ED. We will also conduct qualitative interviews with participants of *ED GOAL*.

- **Provide study schema as applicable (a schema is required for greater than minimal risk studies, and optional for minimal risk studies)**

4. Subject Selection

Describe sources of subjects and procedures for subject selection, including the following:

- **Inclusion/Exclusion Criteria**

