EMR documentation (primary outcome)	Review EMR to see if new documentation of ACP conversation, change in code status, or advance directive forms documented by physicians or mid-level providers exist.	Baseline & at 1, 6, and 12 months
Self-reported ACP conversation survey (primary outcome)	Quantitative and qualitative questionnaires to assess the self-reported completion of ACP conversations with outpatient clinicians and families as well as barriers/facilitators of this process.	At 1, 3, and 6 months

Heard and understood survey (secondary outcome)	A validated instrument for seriously ill patients to report how well they feel heard and understood about their wishes for end-of-life care. ³¹	Baseline & 1, 3, and 6 months
Quality of communication survey (secondary outcome)	A validated instrument to measure the quality of communication about end-of-life care. ³²	Baseline & at 1, 3, and 6 months
Healthcare utilization (secondary outcomes)	Review EMR to see # of urgent care visits, ED visits, hospitalizations, hospice visits, and outpatient visits.	At 6 and 12 months before and 1, 6, 12 months after enrollment
Mortality	Review EMR to determine patient's vital status.	At 1, 3, and 6 months
Qualitative benefits and obstacles of ACP conversations after ED GOAL (secondary outcome)	Semi-structured interviews to assess the benefits of ED GOAL and obstacles participants faced in completing more ACP conversations with their outpatient clinicians and loved ones after ED GOAL (see interview guide).	At 1, 3, and/or 6 months

- **Description of planned genetic research as applicable (e.g., specific description of whole genome sequencing, creation of immortalized cell lines or induced pluripotent stems cells, and sharing of genetic material with collaborators and central repositories as applicable, etc.)**
Not applicable.
- **Description of plans for return of research results as applicable (e.g., specific description of, rationale for, and process by which research results will be returned, including to whom, by whom, and when, etc.). Include plans for managing incidental findings as applicable.**
Not applicable.
- **Definition of primary and secondary outcomes/endpoints. Note that outcome measures should be quantifiable and measurable.**
Please see **Table 4** above.
- **Definition of study termination criteria, e.g., objective criteria for clinical worsening, lack of improvement, and/or unacceptable adverse events**

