Describe plans for statistical analysis, including:

- **Statistical methods/data analysis plan**

Aim 1 quantitative data analysis:

We will conduct an intention-to-treat analysis. Since the primary outcome is mean change in self-reported ACP engagement, we do not expect differences among patients who are admitted vs. discharged. For our secondary outcome, we suspect that there is a propensity of more ACP documentation in patients who are hospitalized and missingness in patients who are primarily cared for at outside institutions. We will plan to use regression in subgroup analysis for ACP documentation to account for hospitalization status. In addition, we will perform sensitivity analyses to account for clustering by individual outpatient clinicians, palliative care consultations, and cognitive impairment status. We will also perform sensitivity analyses for survey respondents (e.g., patients vs. caregivers). We will compare patient demographics by study arm to assess randomization using bivariable analyses (t-test for continuous variables and chi-square for categorical variables). The mean changes in ACP engagement (primary outcome) at one month will be compared by study arms to estimate effect sizes. Within arms, we will use a one-sample binomial exact test of proportions for categorical outcomes (e.g., EMR documentation), and Wilcoxon signed ranks test for ordinal outcomes (e.g., ACP Engagement Survey) at baseline, after the intervention at one month. A p-value of 0.05 will be the significance threshold. To address missing data, I will conduct a secondary analysis using linear mixed models at baseline and one month. For qualitative outcomes,

Aim 2 qualitative data analysis:

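### The primary between-arm comparison of the ACP engagement score has no stated model, baseline covariate or confidence interval; a baseline-adjusted difference with 95% CI should be primary

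*Combined protocol and SAP*

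**What the plan says.** The Aim 1 analysis text in Section 9 identifies the survey outcome ("Since the primary outcome is mean change in self-reported ACP engagement") and then gives the between-arm comparison: "The mean changes in ACP engagement (primary outcome) at one month will be compared by study arms to estimate effect sizes". Nothing further is said about how that comparison is made.

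Every method the documents name has another job:
- t-test and chi-square: demographics by arm.
- Exact binomial and Wilcoxon signed ranks: within-arm results ("Within arms, we will use a one-sample binomial exact test of proportions for categorical outcomes", with the signed-rank test for ordinal outcomes such as the survey).
- Regression: a subgroup analysis of ACP documentation by hospitalization status.
- Linear mixed model: missing data ("I will conduct a secondary analysis using linear mixed models at baseline and one month"). Its fixed effects and treatment contrast are not stated.
- Fisher's exact test: the power statement only.

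Section 9 also plans sensitivity analyses for clustering by outpatient clinician, palliative care consultation, cognitive impairment status and type of respondent. It sets a 0.05 significance threshold. No confidence interval is planned anywhere in the documents.

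On the baseline score, Section 6 disagrees with itself. The measures table schedules the ACP engagement surveys at baseline and at 1, 3 and 6 months. The description of initial enrollment and Table 3 place the enrollment survey after the intervention.

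**The concern.** The power section says the pilot is not powered for significance and is meant to estimate preliminary effect sizes. Section 1 says the findings will support a proposal for a definitive multi-site trial. The between-arm estimate and its uncertainty are therefore the main quantitative product of Aim 1, yet the plan fixes neither the estimator nor the interval.

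Read literally, the comparison is a difference in mean changes, which uses the baseline score by subtracting it with a fixed slope of 1. A model that estimates the slope uses the same data and is usually more precise. The tests that are spelled out compare each arm with itself, so they do not estimate the effect of ED GOAL against usual care.

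**Working it through.** **Inputs from the documents.** 60 per arm (Section 2); 10% expected deaths, leaving 60 × 0.9 = 54 per arm (Section 9, power analysis); two-sided alpha 0.05; conservative effect size 0.25. The documents do not say which SD the 0.25 refers to.

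**Assumptions.** The correlation r between baseline and one-month scores is not given, so it is varied from 0.3 to 0.8. The SDs at the two times are first taken as equal, then varied. The baseline score is taken before the intervention.

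**The plan's own figure.** The only figure given is 90% power with 60 per group by Fisher's exact test, which does not fit a mean change. As a standardized mean difference of 0.25, 60 per arm gives about 27% power (noncentral t). The 90% is not reproduced, and nothing below uses it.

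**Variance.** With a score SD of 1 at both times:
- change score, per person: 2(1 − r)
- baseline-adjusted (ANCOVA), per person: 1 − r²
- ratio: (1 − r²) / [2(1 − r)] = (1 + r)/2

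**Half-width of the 95% CI** = t × SD × √(2/n), where √(2/54) = 0.1925. For the change score df = 2n − 2 = 106 and t = 1.983. For ANCOVA df = 2n − 5 = 103 (arm, baseline, two cognitive-group terms) and t = 1.983. At r = 0.5:
- change: 1.983 × 1.000 × 0.1925 = 0.38
- ANCOVA: 1.983 × 0.866 × 0.1925 = 0.33

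Results at 54 per arm, in SD of the score, with power for a difference of 0.25 SD:

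| r | Variance ratio | Half-width, change | Half-width, ANCOVA | Power, change | Power, ANCOVA |
|---|---|---|---|---|---|
| 0.3 | 0.65 | 0.45 | 0.36 | 19% | 27% |
| 0.5 | 0.75 | 0.38 | 0.33 | 25% | 32% |
| 0.7 | 0.85 | 0.30 | 0.27 | 38% | 44% |
| 0.8 | 0.90 | 0.24 | 0.23 | 53% | 57% |

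With all 60 per arm and r = 0.5, the half-width goes from 0.36 to 0.31 and power from 27% to 35%. At r = 0.5 with equal SDs, the SD of change equals the SD of the score (√(2 × 0.5) = 1), so these figures hold whichever SD the 0.25 refers to.

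**Unequal SDs.** Let k be the one-month SD divided by the baseline SD. The change-score variance is 1 + k² − 2rk and the adjusted variance is k²(1 − r²). The first minus the second is (1 − rk)², which cannot be negative. Variance reduction:

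| k | r = 0.3 | r = 0.5 | r = 0.7 | r = 0.8 |
|---|---|---|---|---|
| 0.8 | 50% | 43% | 37% | 36% |
| 1 | 35% | 25% | 15% | 10% |
| 1.25 | 22% | 11% | 2% | 0% |

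The gain vanishes when rk = 1, where subtraction is already the best use of baseline. The only cost then is three degrees of freedom, which is trivial at this sample size.

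**Bias.** In 20,000 simulated trials with 54 per arm and no effect, both estimators were biased by less than 0.002 SD. The simulated variance ratios were 0.667, 0.755 and 0.863 at r = 0.3, 0.5 and 0.7, close to the formula.

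**The case against.** The strongest reply is that this is an efficiency preference. A change-score comparison is valid under randomization, the pilot disclaims power, and power for 0.25 SD stays low after adjustment (32% at r = 0.5). No conclusion of the pilot is shown to change. That stands as far as the choice between ANCOVA and change score goes. It does not answer the missing interval: a study whose product is an effect size needs a stated estimator and a statement of uncertainty, whatever r turns out to be.

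A second reply is that the plan already contains a suitable model. This is partly right. A reader might infer that baseline is used only by subtraction, but the mixed model at baseline and one month also uses it. If baseline means are constrained equal across arms, such a model recovers essentially the ANCOVA precision; without that constraint it does not. As written it is secondary and its terms are unstated, so it does not yet supply the primary analysis. Likewise, the sensitivity analyses for cognitive status and respondent partly address those factors without defining the primary contrast.

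Third, the plan does not call the comparison unadjusted. That is an inference from silence; the firm statement is that no method is specified.

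A reader might also infer that the within-arm tests are meant as the test of efficacy. The documents do not say so, and they do plan a between-arm comparison.

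**Conclusion.** The point holds as a gap in specification and a loss of precision. The primary between-arm comparison of the survey score lacks a model, a baseline covariate and a confidence interval. With r assumed at 0.3 to 0.8 and equal SDs, baseline adjustment lowers the variance by 35% to 10%. The gain is smaller if the one-month SD exceeds the baseline SD, larger if it is lower, and never negative apart from a trivial loss of degrees of freedom. The need for an interval does not depend on r.

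The documents do not support a claim that the planned contrast is biased or invalid. There is one exception to watch: if the enrollment survey really follows the intervention, either subtracting that score or adjusting for it would distort the effect, so the timing conflict matters under both analyses.

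The inconsistent labelling of the primary outcome (Section 2 hypothesis, Section 6 measures table, Section 9), the analysis population, the power statement and the scoring of patient-caregiver pairs are separate matters and add no weight here. The revision should be made; the diagnosis is firmer than the exact size of the gain.

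**What to change.** First reconcile the initial enrollment text and Table 3 with the measures table in Section 6, so that the baseline ACP engagement score is taken before the intervention in both arms.

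Then revise the Aim 1 analysis in Section 9:
- Make the primary analysis of the survey score an ANCOVA of the one-month score on arm, baseline score and cognitive group (the three groups into which participants are classified before randomization). Alternatively, promote the planned linear mixed model, state its terms and constrain baseline means to be equal across arms.
- Report the adjusted between-arm difference with its 95% CI as the main result.
- Label the within-arm tests as descriptive.
- Keep the planned sensitivity analyses for cognitive status and respondent.

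The cost is a few sentences in Section 9 and one correction in Section 6. No new data are needed if the scheduled baseline survey precedes the intervention. If the enrollment text and Table 3 describe what will be done, one survey must be moved or added.

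### For the ACP Engagement Survey the analysis section tests change only within each arm; the between-arm comparison that Aim 1 hypothesises has no named test or confidence interval.

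*Combined protocol and SAP*

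**What the plan says.** Section 2 states the Aim 1 hypothesis as a comparison of arms: ACP engagement "will significantly increase in those who received *ED GOAL* compared to usual care". The design is randomised: "Pilot test, in a randomized controlled design (N=120, 60 in each group". The hypothesis is worded for a composite of patient-reported and EMR outcomes. Section 9 takes the mean change in self-reported engagement as the primary outcome and gives no analysis of a composite.

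Section 9 (Statistical Analysis, Aim 1 quantitative data analysis) treats the survey score in four steps:

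- Between arms: "The mean changes in ACP engagement (primary outcome) at one month will be compared by study arms to estimate effect sizes". No test, model or interval is named.
- Within each arm: "Wilcoxon signed ranks test for ordinal outcomes (e.g., ACP Engagement Survey", applied to baseline and one month.
- Threshold: "A p-value of 0.05 will be the significance threshold". The sentence does not say which tests it governs.
- Missing data: "To address missing data, I will conduct a secondary analysis using linear mixed models at baseline and one month". No arm-by-time term or other arm contrast is stated.

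The t-test and chi-square test in the same section are for comparing demographics by arm. The power analysis adds a two-sided Fisher's exact test at 0.05. It also says that the pilot is not powered for significant differences and that the arms will be compared at 1, 3 and 6 months to estimate preliminary effect sizes.

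**The concern.** The hypothesis is about a difference between arms, but the p-values that the analysis section assigns to the survey score are one per arm. Each asks whether scores moved from baseline in that arm. Each therefore picks up any change common to both arms: repeated administration of the survey, regression to the mean, the ED event itself, or ACP under usual care. Some usual-care change is plausible on the protocol's own account, because Sections 4 and 7 describe ACP conversations as routine for these patients and for ED clinicians.

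Section 1 says the trial is randomised because the earlier improvement came from a one-arm before-after study. A before-after test in each arm repeats that earlier analysis twice. With no between-arm p-value or interval specified, a reader of the results could be left to compare one significant arm with one non-significant arm. The findings are meant to support a proposal for a larger trial, so a misleading contrast would carry forward.

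**Working it through.** **The plan's own figure.** The nearest stated figure is 90% power with 60 per group, using a two-sided Fisher's exact test and a conservative effect size of 0.25. It does not reproduce for a mean difference: a standardised difference of 0.25 gives 27.7% power at 60 per arm and 25.4% at 54. Fisher's test for a 25-point difference in proportions at 60 per arm gives 88.7% if the control rate is 10% and 75.7% if it is 26%. So the figure comes near 90% only when 0.25 is read as a difference in proportions with a control rate near 10%, which the documents do not give. This is a separate matter and does not enter the calculation below. It does show that the Fisher test supplies no test of the survey score.

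**Inputs.** From the documents: 60 per arm; 10% expected deaths, so 60 x 0.90 = 54 per arm; two-sided threshold 0.05; Wilcoxon signed-rank test within each arm. Assumed: normal change scores, independent arms, and the same true standardised change in both arms, so that there is no arm difference. The size of that shared change is varied because the documents do not give it.

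**Formula.** P(significant increase in ED GOAL, not significant in usual care) = P(significant increase) x [1 - P(significant)]. Once the shared change is large enough for significant decreases to be negligible, this is p(1 - p), where p is the within-arm power. It cannot exceed 0.5 x 0.5 = 0.25.

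**Results.** Within-arm power was simulated with 20,000 runs per setting.

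| Shared change (SD) | Power, n=60 | ED GOAL only, n=60 | Power, n=54 | ED GOAL only, n=54 |
|---|---|---|---|---|
| 0 | 0.051 | 0.024 | 0.049 | 0.022 |
| 0.10 | 0.116 | 0.099 | 0.109 | 0.093 |
| 0.20 | 0.317 | 0.216 | 0.282 | 0.202 |
| 0.25 | 0.463 | 0.249 | 0.424 | 0.244 |
| 0.30 | 0.606 | 0.239 | 0.565 | 0.246 |
| 0.40 | 0.848 | 0.129 | 0.808 | 0.155 |
| 0.50 | 0.962 | 0.036 | 0.941 | 0.055 |

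Worked examples: at 0.25 SD and n=54, 0.424 x 0.576 = 0.244. At 0.50 SD and n=60, 0.962 x 0.038 = 0.037, against 0.036 from unrounded values. With no change in either arm, the nominal rate is 0.05 x 0.95 = 0.0475 if a significant change in either direction counts.

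**Cross-check.** Paired t-test power at 0.25 SD is 0.478 (n=60) and 0.438 (n=54), giving p(1 - p) = 0.250 and 0.246.

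**Benchmark.** A valid two-sided between-arm test at 0.05 would favour ED GOAL wrongly 2.5% of the time, whatever the shared change.

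**The case against.** The strongest reply is that the plan does compare the arms. Section 9 sets mean change in one arm against the other and repeats the intention for 1, 3 and 6 months. It says the pilot is not powered for significance and aims at effect sizes. Section 3 describes the design as including pre-/post-intervention assessment, so within-arm change is a legitimate thing to report. Nowhere does the plan say that efficacy will be concluded from significance in one arm and not the other.

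All of that stands, and it rules out two readings that might be inferred. One is that the plan discards its control arm: it does not, because a between-arm effect size is planned. The other is that the Wilcoxon test is the only test mentioned anywhere that could bear on the arms. Fisher's test is named in the power paragraph, and the mixed model could yield an arm contrast if one were specified.

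The reply does not close the gap. Pilot status argues for a between-arm estimate with an interval, and none is named. It is no argument for testing each arm at 0.05. Fisher's test is for proportions, and the mixed model is offered only for missing data. The hypothesis of a significant increase over usual care therefore remains without a specified test.

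**Conclusion.** The point holds as a gap in specification: the significance test assigned to the survey score in the analysis section does not address the hypothesis in Section 2, and the comparison that would address it has no test or interval. Its consequence is conditional on readers or authors judging the arms by the within-arm p-values. In that case, with no arm difference, the chance of significance in ED GOAL only is about 2-5% if neither arm changes, about 9-10% if both improve by 0.10 SD, at most about 25% if both improve by 0.25-0.30 SD, and about 4-6% if both improve by 0.50 SD.

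A reader might take one in four as the expected error rate. The documents do not support that. It is the ceiling of p(1 - p), reached only when within-arm power is near 50%. The plan's 0.25 is a conservative effect size derived from the earlier ED GOAL result, and it is not presented as a change shared by usual care. The calculation also assumes normal change scores and 54-60 analysed per arm. The recommendation does not depend on which scenario is true, since the within-arm tests fail to answer the between-arm question in all of them. The plan should be changed, and the change is one of wording.

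**What to change.** In Section 9:

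1. Make the primary survey analysis the between-arm difference in one-month change, reported with a 95% CI. Name one estimator, for example ANCOVA of the one-month score on arm and baseline score, or the arm-by-time term of the mixed model already planned.
2. Apply the 0.05 threshold for the survey score only to that contrast.
3. Replace the within-arm Wilcoxon tests with within-arm mean change and 95% CI, labelled descriptive.
4. State that no conclusion about ED GOAL rests on within-arm change.

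Any of these estimators needs a baseline score taken before the intervention. The measures table in Section 6 lists a baseline survey, but the visit description and Table 3 mention only questionnaires after ED GOAL at enrolment, so the timing should be stated in the same edit.

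The cost is a few sentences in the analysis section. No extra data, visits or participants are needed.

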Our intervention is followed by scheduled, follow-up visits at one, three, and six months afterwards. The follow-up visits will be performed to assess the outcomes as well as to serve as the ACP care navigation/coaching by our study clinician.

Study clinician training:

We will train the study clinicians to administer these tools by 3-hour didactic on the concepts of delirium, cognitive impairment, and dementia, as well as bedside practice administration with the PI until competency is demonstrated (PI will self-record the responses next to the study clinician administering the instrument and compare the results. We will repeat this process with new patient volunteers until there is no discrepancy). In the case of equivocal findings on these assessments administered by study clinician, the PI backup will be available.

Intervention fidelity:

To ensure that all study clinicians deliver our intervention consistently, we will check the intervention fidelity. The percent adherence to the intervention fidelity checklist will be measured for every participant encounter (see attached fidelity checklist). High fidelity will be defined as mean adherence of >70% to the components on the fidelity checklist, which is consistent with expert consensus for behavioral intervention studies.²⁸

- **Justification and safety information if FDA approved drugs will be administered for non-FDA approved indications (“off-label”): How are doses, routes of administration, or participant populations different from FDA approved indicated use?**

Not applicable.

- **Description of specific data variables to be collected, including data collection methods, assessments, data collection sheets, and/or schedule of assessments (A schedule/table of study assessments is preferred)**

Measures	Descriptions	Timing
ACP engagement survey for patients (primary outcome)	Used for patients , this validated instrument will measure the self-reported processes for ACP (knowledge, contemplation, self-efficacy, and readiness), and ACP behavior. ²⁹	Baseline & at 1, 3, and 6 months
ACP engagement survey for caregivers (primary outcome)	Used for surrogate decision-makers , this ACP engagement survey is validated to measure the same ACP processes and behaviors. ³⁰	Baseline & at 1, 3, and 6 months

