We will conduct in-depth, semi-structured interviews with participants. We will explore the perceived benefits of the intervention as well as barriers to completing ACP conversations after leaving the ED. The interviews will be recorded and professionally transcribed. The transcripts will be analyzed to identify recurring themes that illustrate the qualitative benefits (e.g., how the intervention changed their lives) and barriers to completing ACP conversations (e.g., how attempted ACP conversations were unsuccessful). Transcripts will be analyzed by two trained researchers to ensure interpretive integrity and consistency per standard comprehensive qualitative analysis methods. We will use framework analysis as the analytic approach,³³ which allows the flexibility of incorporating *a priori* considerations as well as more emergent themes in the data. The coding structure will be collaboratively and iteratively developed by the research team and include both prefigured and emergent codes.³⁴ We will use an ethnographic data management software program, NVivo 10 (QSR International). If there are disagreements, the mentors/advisors and we will review the quotes and themes to discuss their meaning and to achieve consensus. We will follow the consolidated criteria for reporting qualitative research.³⁵

- **Power analysis (e.g., sample size, evaluable subjects, etc.)**

For Aim 1 (quantitative data):

While this pilot RCT study is not powered to detect statistically significant differences in the ACP outcomes, we will compare 1-, 3-, 6-month ACP outcomes in the intervention arm to the control arm to estimate the preliminary effect sizes. Our prior study demonstrated a mean patient-reported ACP engagement increased from 3.8 to 4.3 on a 5-point scale, corresponding to a moderate effect size of 0.50.³⁶ A conservative estimate of effect size is 0.25. We also expect that 10% of enrolled patients will die before completing all follow-ups. With a sample size of 60 patients per group, we would have 90% power to detect the difference using a 2-sided Fisher's exact test ($\alpha=0.05$). We plan to exclude patients who die before 6-month in the analysis.

For Aim 2 (qualitative data):

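### The only missing-data model covers baseline and one month, so it makes no use of the 3- and 6-month surveys and leaves the later arm comparisons with no stated method for missing scores

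*Combined protocol and SAP*

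**What the plan says.** Section 9 (Aim 1 quantitative data analysis) sets the primary comparison: "The mean changes in ACP engagement (primary outcome) at one month will be compared by study arms to estimate effect sizes". It states the principle "We will conduct an intention-to-treat analysis" and gives one method for missing data: "To address missing data, I will conduct a secondary analysis using linear mixed models at baseline and one month".

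The measures table in Section 6 schedules the patient and the caregiver engagement surveys at "Baseline & at 1, 3, and 6 months". The power analysis in Section 9 says "we will compare 1-, 3-, 6-month ACP outcomes in the intervention arm to the control arm to estimate the preliminary effect sizes".

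On losses, the same section says "We also expect that 10% of enrolled patients will die before completing all follow-ups" and "We plan to exclude patients who die before 6-month in the analysis". The documents give no rate for withdrawal or non-response among survivors. The sensitivity analyses listed in Section 9 concern clustering by outpatient clinician, palliative care consultation, cognitive status and type of respondent. The one other remark on missingness concerns record documentation for patients cared for elsewhere, and no missing-data method is attached to it.

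**The concern.** Two of the three planned comparisons have no stated way of handling missing scores, and the model that exists uses two of the four scheduled visits. There are two consequences.

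- A participant who misses the one-month call but answers later gives this model a baseline score only, although the later scores carry information about the missing one.
- A participant who answers at one month and is then lost would be absent from an available-case comparison at 3 or 6 months, although the one-month score helps to predict what is missing.

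The pilot's product is a set of effect estimates for a larger trial proposal (Section 1). If participants who had not progressed by one month stopped answering more often in one arm, the later estimates could be distorted. A likelihood-based model with all visits corrects for loss that depends on scores already observed. It does not correct for loss that depends on unobserved scores.

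**Working it through.** **Inputs from the documents.** 60 participants per arm (Section 2); visits at baseline, 1, 3 and 6 months (Section 6); conservative effect size 0.25 and 10% deaths (Section 9). Deaths alone take 0.10 × 120 = 12, leaving 108, or 54 per arm if split evenly. The plan states no figure on this point that could be reproduced. Its 90% power statement is a separate matter and is not used here.

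**Assumptions, not in the documents.** Score SD 1; equal correlation ρ between visits of 0.4 to 0.8; 5% to 20% missing at one month; 10% to 40% lost by month 6.

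**1. One-month contrast.** Adjusted for baseline, with n observed per arm, SE = √[2(1 − ρ²)/n].
- With ρ = 0.6 and 20% missing (n = 48): √(2 × 0.64/48) = 0.163.
- Given baseline, the correlation between two follow-up scores is r = (ρ − ρ²)/(1 − ρ²) = 0.24/0.64 = 0.375.
- Scores at 3 and 6 months then explain R² = 2r²/(1 + r) = 0.281/1.375 = 0.20 of the remaining variance at one month. This is the share of the lost information that they recover. For ρ = 0.4 it is 13%, and for ρ = 0.8 it is 27%.
- SE with all visits = √{2 × 0.64 × [(1 − 0.2045)/48 + 0.2045/60]} = 0.160, so 0.163 falls to 0.160.

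**2. Six-month contrast, precision.** The comparator is baseline-adjusted available cases. Loss is in two equal steps, the first before month 3 and the second before month 6.

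| ρ | Lost by month 6 | SE, baseline and month 6 only | SE, all visits | Reduction |
|---|---|---|---|---|
| 0.4 | 10% | 0.1764 | 0.1755 | 0.5% |
| 0.6 | 40% | 0.1886 | 0.1816 | 3.7% |
| 0.8 | 40% | 0.1414 | 0.1343 | 5.0% |

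**3. Six-month contrast, bias in an adverse scenario.** True effect 0.25 SD. In the ED GOAL arm, 25% of those with below-average one-month change are lost and 5% of the rest (15% overall). In the control arm 15% are lost, unrelated to score.
- Shift in one-month change among those retained: 0.798 × (0.95 − 0.75)/(0.95 + 0.75) = 0.094 SD of change, where 0.798 = √(2/π).
- The correlation between 1- and 6-month change is (1 − ρ)/[2(1 − ρ)] = 0.5. With ρ = 0.6 the SD of change is √(2 × 0.4) = 0.894.
- Bias = 0.094 × 0.5 × 0.894 = 0.042 SD, which is 0.042/0.25 = 17% of the conservative effect. For ρ from 0.8 to 0.4 it is 0.03 to 0.05.
- With 60 × 0.85 = 51 per arm, the SE of the difference in change is 0.894 × √(2/51) = 0.177, and 0.042/0.177 = 0.24.
- A simulation at ρ = 0.6 gives 0.29 for available-case change, 0.28 for available cases adjusted for baseline, and 0.25 when the one-month score is used.

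**4. Other dropout patterns.**
- Loss with the same pattern and rate in both arms, or unrelated to earlier scores: bias about nil.
- Loss driven by the one-month score rather than the change, at 20% to 30% against 10%: unadjusted change stays at about 0.25 under equal correlations. Available cases adjusted for baseline give 0.27 to 0.29, and all visits about 0.25.
- The direction can reverse. With selection on the score in one arm giving a shift of 0.094, and correlations of 0.7 (baseline to month 1) and 0.5 (month 1 to month 6), the bias in change is 0.094 × (0.5 − 0.7) = −0.02 SD.

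**The case against.** The strongest defence is that the missing-data analysis matches the primary time point. Aim 1, the study design and the primary comparison are all at one month, and the power section says that the pilot is not powered and is estimating preliminary effect sizes. This stands: extending the model is a refinement and does not correct an error in the primary analysis.

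A reader might infer three stronger things that the documents do not support.

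- That later scores from people who miss the one-month call are discarded. They are unused only in the one-month mixed model; they still enter the planned 3- and 6-month comparisons.
- That the later comparisons are specified as completer analyses. No method is stated for them. Available cases are the likely default, and only the exclusion of deaths is explicit.
- That withdrawal is known to be heaviest at the later visits. The only loss figure is 10% deaths, and the eligibility table excludes patients who cannot or will not schedule follow-ups.

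It can also be said that the change is not just a matter of wording, and this too stands. Patients and caregivers complete separate instruments, and in the mild impairment group both respond (Table 2). As-needed coaching is listed as intervention at each follow-up (Table 3), so a covariance common to both arms needs justification. Nor would an all-visit model settle how deaths are treated.

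**Conclusion.** The point holds as an inexpensive improvement. The only missing-data model stops at one month, and the 3- and 6-month comparisons have no stated method for missing scores.

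The expected benefit is modest: a 6-month standard error about 0.5% to 5% lower and, in the adverse scenario, removal of about 0.04 SD of bias, a quarter of a standard error. That bias requires dropout that differs by arm and depends on earlier change. Quoting it as 17% of the conservative effect, without the standard error beside it, would make it look larger than it is. All these sizes rest on assumed correlations and dropout rates, because the documents give neither.

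The exclusion of patients who die before 6 months is a related but separate issue. Read literally, it could remove one-month scores already observed from patients who die between months 1 and 6, which sits badly with the intention-to-treat statement.

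**What to change.** - Extend the time points of the planned mixed model to baseline, 1, 3 and 6 months. Use arm, visit and arm-by-visit terms with an unstructured covariance, and include every observed score before and after a missed visit.
- Fit it to each respondent's own instrument. Do not pool patient and caregiver scores without a stated rule.
- Justify a covariance common to both arms, or check the result with arm-specific covariances.
- Report the arm difference with a 95% confidence interval at each visit, and the number missing by arm, visit and reason (death, withdrawal, not reached). Keep the one-month comparison as primary.
- Reconcile the death exclusion with the intention-to-treat statement, so that scores observed before death are kept and estimates are not read as applying after death.

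The data are already scheduled for collection and participants carry no extra burden. The cost is a revised paragraph, a little programming, and two decisions made before the data are seen: the rule for the two instruments and the handling of deaths.
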